5.5.3 Laboratory Parameters

This section provides further detail on the analysis of laboratory parameters that will be listed and summarized as described in [Section 2.8.3](#).

Hematology

Hematologic tests include Hemoglobin, platelets, white blood cells (WBC) with differentials (basophils, eosinophils, lymphocytes, monocytes, neutrophils (% or absolute))

The following rules will be applied to derive the WBC differential counts when only percentages are available (this is mainly for neutrophils and lymphocytes, because CTC grading is based on the absolute counts).

The method to convert the value is straightforward: for each subject, the original lab value (%) is divided by 100 and multiplied by WBC count e.g. for neutrophils (NEU):

$$\text{NEU count} = (\text{WBC count}) * (\text{NEU\%value}/100)$$

In order to derive the corresponding absolute normal range, the rule to be applied depends on the availability of the % range and the absolute range for the differential:

- If % absolute range NOT missing (% range is or isn't missing), then use the absolute range provided by the site
- If % range NOT missing and absolute range missing, then the % normal limits (i.e. LLN and ULN) are divided by 100 and multiplied by the corresponding normal limits of WBC count, e.g. for neutrophils NEU):

$$\text{LLN for NEU count} = (\text{LLN for WBC count}) * (\text{LLN for NEU\%value} / 100)$$

$$\text{ULN for NEU count} = (\text{ULN for WBC count}) * (\text{ULN for NEU\%value}/100)$$

Biochemistry

The following calculation will be applied for corrected calcium in SI unit:

Corrected calcium (mmol/L) = measured total Ca (mmol/L) + 0.02 (40 - serum albumin[g/L]), where 40 represents the average albumin level in g/L.

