**Table 6-4 Criteria for interruption and re-initiation of LDK378 treatment**

| Worst toxicity (CTCAE 4.03 Grade)*  | Dose Modifications for LDK378   |
|--|--|
| HEMATOLOGICAL   |  |
| Neutropenia (ANC)   |  |
| Grade 1 (ANC < LLN - $1.5 \times 10^9/L$ )
Grade 2 (ANC < 1.5 and $\geq 1.0 \times 10^9/L$ )
Grade 3 (ANC < 1.0 and $\geq 0.5 \times 10^9/L$ )                       | Maintain dose level  |
| Grade 4 (ANC < $0.5 \times 10^9/L$ )   | Omit dose until resolved to $\leq$ Grade 2, then:
If resolved in $\leq 7$ days, then maintain dose level
If resolved in $> 7$ days, then $\downarrow 1$ dose level |
| Febrile neutropenia
(ANC < $1.0 \times 10^9/L$ , with a single temperature of $\geq 38.3$ °C or a sustained temperature of $\geq 38$ °C for more than one hour ) | Omit dose until clinically resolved and neutropenia $\leq$ Grade 2, then $\downarrow 1$ dose level   |
| Thrombocytopenia  |  |
| Grade 1 (PLT < LLN - $75 \times 10^9/L$ )
Grade 2 (PLT < 75 and $\geq 50 \times 10^9/L$ )   | Maintain dose level  |
| Grade 3 (PLT < 50 and $\geq 25 \times 10^9/L$ )  | Omit dose until resolved to $\leq$ Grade 2, then:
If resolved in $\leq 7$ days, then maintain dose level
If resolved in $> 7$ days, then $\downarrow 1$ dose level |
| Grade 4 (PLT < $25 \times 10^9/L$ )  | Omit dose until resolved to $\leq$ Grade 2, then $\downarrow 1$ dose level   |
| HEPATIC   |  |
| Alkaline phosphatase and/or Gamma-glutamyl transpeptidase (GGT)   |  |
| Isolated elevations of any grade   | Maintain dose level  |
| Total Bilirubin**
(for patients with Gilbert Syndrome these dose modifications apply to changes in direct [conjugated] bilirubin only)                           |  |
| Grade 1 ( $> ULN$ and $\leq 1.5 \times ULN$ )  | Maintain dose level with liver function test (LFTs)*** monitored as per protocol   |

| Worst toxicity (CTCAE 4.03 Grade)*   | Dose Modifications for LDK378  |
|---|---|
| Grade 2 (> 1.5 and ≤ 3.0 x ULN) with ALT or AST ≤ 3.0 x ULN   | Omit dose until resolved to ≤ Grade 1, then:
If resolved in ≤ 7 days, then maintain dose level
If resolved in > 7 days, then ↓ 1 dose level   |
| Grade 3 (> 3.0 and ≤ 10.0 x ULN) with ALT or AST ≤ 3.0 x ULN  | Omit dose until resolved to ≤ Grade 1, then:
If resolved in ≤ 7 days, ↓ 1 dose level
If resolved in > 7 days, discontinue patient from LDK378 |

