#### 10.7.1.3 Laboratory abnormalities

All laboratory values will be converted into SI units, as appropriate, and the severity grade calculated using CTCAE, version 4.03. Parameters for which a grading does not exist will be classified into low/normal/high group by means of laboratory normal ranges.

For each laboratory test (e.g. hematology, biochemistry etc.) a listing of laboratory values will be provided by laboratory parameter, patient and treatment group. The frequency of notable lab abnormalities (i.e. newly occurring CTCAE grade 3 or 4 laboratory toxicities), will be reported by parameter, cycle and treatment group. Similarly, the frequency of all laboratory abnormalities will be tabulated by parameter, worst CTCAE v4.03 grade experienced, and treatment group. Laboratory data will be summarized by presenting grade shift tables for those parameters that can be classified using CTCAE version 4.03. All remaining data will be summarized by presenting shift tables based on normal ranges.

Laboratory data will be also be displayed by presenting summary statistics of raw data and change from baseline values (means, medians, standard deviations, ranges).

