2.8.2 Laboratory data

The summaries will include all laboratory assessments collected no later than 30 days after last dose of study drug. All laboratory assessments will be listed and those collected later than 30 days after study drug discontinuation will be flagged in the listings. For laboratory data assessments, data from all sources (central and local laboratories) will be combined.

Laboratory data will be classified (by Novartis Oncology CDRR) into CTC grades according to the National Cancer Institute (NCI) CTCAE v4.03. For all reports, CTC grade is always obtained on the converted measurement in SI unit. Grade 5 will not be used. The CTC grade 0 will be assigned as below in different scenarios:

1. For lab parameters defined by criteria based on normal range only, a severity grade of 0 will be assigned when the value is within normal limits.
2. For lab parameters whose grade is defined by criteria based on normal range and absolute values (e.g. platelet count decrease). A severity grade of 0 will be assigned when the value is within normal limits.
3. For lab parameters whose grade is defined by criteria based on normal range and the change from baseline value, with no other associated clinical criteria such as concomitant medication (e.g. creatinine increased) the following will be applied. For the baseline grading and for the grading of post-baseline laboratory values with missing baseline grading, the grade will be derived using the criteria based only on the normal range as per CTCAE v4.03. A severity grade of 0 will be assigned when the post-baseline value is \leq ULN (for hyper) or \geq LLN (for hypo).

Parameters for which a grading does not exist will be classified into low/normal/high group by means of laboratory normal ranges.

The following summaries will be produced for laboratory data (by laboratory parameter):

- Shift tables using CTC grades to compare baseline to the worst post-baseline value for laboratory parameters with CTC grades.
- Shift tables using low, normal, high (as well as low and high combined) classifications to compare baseline to the worst post-baseline value for laboratory parameters where CTC grades are not defined.

Liver function tests (LFTs) of interest for LDK378 are total bilirubin (TBILI), ALT, AST and ALP. In what follows, AT refers to ALT or AST values. LFTs will be summarized as follows:

- Shift tables of baseline vs. worst post-baseline on-treatment values for the categories:

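### SAP 2.8.2 grades any neutrophil count within normal limits as 0, with no override by the absolute cut-offs, and the limit that SAP 5.5.3 derives from percentages can be low enough to hide grade 2 or 3 neutropenia

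*SAP*

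**What the plan says.** Protocol 10.7.1.3 sets the standard: "All laboratory values will be converted into SI units, as appropriate, and the severity grade calculated using CTCAE, version 4.03". Protocol Table 6-4 shows how neutropenia is graded. Grade 1 runs from the lower limit of normal (LLN) down to 1.5 x10^9/L. Below that the boundaries are fixed: "Grade 2 (ANC < 1.5 and" at least 1.0, grade 3 from below 1.0 to 0.5, and grade 4 below 0.5.

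SAP 2.8.2 then defines grade 0. Its second scenario reads "For lab parameters whose grade is defined by criteria based on normal range and absolute values (e.g. platelet count decrease"), and it uses the same rule as the first scenario: "a severity grade of 0 will be assigned when the value is within normal limits". Neutrophils are not named, but Table 6-4 gives them exactly this structure. Nothing says that a value below a fixed cut-off keeps its grade when it is also inside the range.

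SAP 5.5.3 explains where the range comes from when a laboratory reports differentials as percentages: "The following rules will be applied to derive the WBC differential counts when only percentages are available", mainly for neutrophils and lymphocytes, "because CTC grading is based on the absolute counts". If the site provides an absolute range, that range is used. Where the site gives only a percentage range, the SAP constructs an absolute one: "the % normal limits (i.e. LLN and ULN) are divided by 100 and multiplied by the corresponding normal limits of WBC count", lower with lower and upper with upper.

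**The concern.** Two rules act together. The first lets the normal range outrank the fixed cut-offs. The second can supply a range that no laboratory ever established and whose lower limit is too low. A count of 0.90 could then be grade 3 under Table 6-4 and grade 0 in the study report.

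Laboratory change is a named secondary safety endpoint (Protocol Table 3-1). The adverse event tables need not make good the loss. Table 6-4 keeps the dose unchanged for grades 1 to 3, and Protocol 8.1.1 counts a laboratory abnormality as an adverse event only if it causes signs or symptoms, is clinically significant, or needs therapy or a change in study medication. For uncomplicated grade 2 or 3 neutropenia the laboratory tables may be the only summary. Such counts can occur even at entry, since the ANC exclusion in Protocol 5.3 is below 0.75. Ranges come from each local laboratory (Protocol 7.2.2.5), so any misgrading would differ by site.

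**Working it through.** Neither document states a figure on this point, so there is nothing to reproduce. I coded the two SAP rules and compared them with applying the absolute cut-offs first.

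**Inputs from the documents.** Count = WBC x NEU%/100, and derived limit L = LLN(WBC) x LLN(NEU%)/100 (SAP 5.5.3). Grade 0 if within limits (SAP 2.8.2). Cut-offs 1.5, 1.0 and 0.5 x10^9/L (Protocol Table 6-4).

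**Assumed inputs, not in the documents.** LLN(WBC) 4.0 to 6.0 x10^9/L; LLN(NEU%) 15 to 45%, with the low end standing for young children.

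**Step 1: when a grade is hidden.** Grade 2 counts from L upwards become grade 0 when L < 1.5, that is, when LLN(NEU%) < 150/LLN(WBC). Grade 3 is reached when LLN(NEU%) < 100/LLN(WBC), and grade 4 when it is < 50/LLN(WBC).

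| LLN(WBC) | Grade 2 hidden if LLN(NEU%) below | Grade 3 hidden if below | Grade 4 hidden if below |
|---|---|---|---|
| 4.0 | 37.5% | 25.0% | 12.5% |
| 4.5 | 33.3% | 22.2% | 11.1% |
| 5.0 | 30.0% | 20.0% | 10.0% |
| 5.5 | 27.3% | 18.2% | 9.1% |
| 6.0 | 25.0% | 16.7% | 8.3% |

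The smallest product in the assumed grid is 4.0 x 15/100 = 0.60, so grade 4 is never hidden there.

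**Step 2: individual counts.**

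| Assumed limits | L | Count | Cut-offs first | SAP rule |
|---|---|---|---|---|
| 5.0 and 15% | 0.75 | 5.0 x 18% = 0.90 | 3 | 0 |
| 5.0 and 15% | 0.75 | 6.0 x 20% = 1.20 | 2 | 0 |
| 5.5 and 20% | 1.10 | 5.5 x 24% = 1.32 | 2 | 0 |
| 4.5 and 40% | 1.80 | 4.0 x 30% = 1.20 | 2 | 2 |

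**Step 3: why the derived limit is too low.** Suppose log WBC and the log percentage are normal with SDs s1 and s2 and correlation r. The product of the two 2.5th percentiles lies 1.96(s1 + s2) below the mean on the log scale. The true 2.5th percentile of the count lies only 1.96 x sqrt(s1² + s2² + 2·r·s1·s2) below it, which is less unless r = 1.

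A simulation of 1,000,000 draws gives the size. It assumed lognormal WBC with median 9 and a logit-normal neutrophil fraction with logit mean -0.3. Log and logit SDs were 0.28 and 0.6 in setting A, and 0.25 and 0.4 in setting B.

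| r | A: L | A: true 2.5th percentile | A: % below L | B: L | B: true 2.5th percentile | B: % below L |
|---|---|---|---|---|---|---|
| -0.3 | 0.97 | 1.66 | 0.10 | 1.39 | 2.11 | 0.06 |
| 0 | 0.97 | 1.43 | 0.38 | 1.39 | 1.88 | 0.30 |
| 0.3 | 0.97 | 1.26 | 0.89 | 1.39 | 1.70 | 0.79 |
| 0.6 | 0.97 | 1.11 | 1.51 | 1.40 | 1.56 | 1.45 |

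Between 0.06% and 1.51% of reference values fall below the derived limit, against the nominal 2.5%. In setting A with r of 0 or more, the correct limit is itself below 1.5. A correct range would then still hide part of grade 2, so the grade 0 rule in SAP 2.8.2 is the root and the product in 5.5.3 aggravates it.

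**The case against.** The best defence is that this is a declared convention. Grade 1 runs from the LLN to 1.5, which has no meaning when the LLN is below 1.5, and calling a value within the laboratory's own range grade 0 is a reasonable way out. Grading on cut-offs alone would label some healthy children grade 2. That defence carries weight for a genuine reference range. It fails for the derived one, which describes no reference population. It also sits badly with Protocol 10.7.1.3, which promises CTCAE grading, and SAP Table 4-1 lists no departure from it.

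Other parts of the defence stand, and they bar several stronger readings.

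- A reader might infer that every laboratory reporting only percentages is affected. The product is used only when the percentage range is present and the absolute range is missing, and Protocol 7.2.2.5 asks sites for the normal ranges of each required parameter. Nothing shows that any site met both conditions.
- A reader might infer that neutropenia in young children is lost as a rule. That needs low percentage limits, which the documents do not give.
- A reader might extend the size to lymphopenia. The derivation covers lymphocytes, but neither document prints lymphocyte cut-offs, so no size can be given.
- A reader might fear for the primary endpoint. The neutropenia DLT in Protocol Table 6-2 needs grade 4 lasting more than 7 days, and dose rules are written in absolute counts.

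The raw values also stay visible in the full laboratory listing, though they would carry the hidden grade.

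**Conclusion.** The point holds as a stated rule that can give a wrong grade. Whenever the lower limit in use is below 1.5 x10^9/L, grade 2 counts at or above it are tabulated as grade 0; below 1.0, so are some grade 3 counts. This follows from the documents alone, given that neutrophils fall under the second scenario of SAP 2.8.2.

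How often it happens cannot be estimated. The percentage thresholds in the working rest on assumed WBC limits, and with adolescent-type limits such as 4.5 and 40% the rule does no harm. The outputs at risk are the CTC shift tables, in both the baseline and worst post-baseline grades, and the grade 3/4 laboratory listing. No product in the assumed grid reaches the grade 4 threshold, so the estimation of the MTD is essentially unaffected. This should be corrected, but it does not threaten the trial's main conclusion.

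**What to change.** In the second scenario of SAP 2.8.2, state that neutropenia grades 2 to 4 are assigned first from the CTCAE v4.03 absolute cut-offs, and that the LLN, whether derived or supplied by the site, serves only to separate grade 0 from grade 1. Add a cross-reference in SAP 5.5.3. Placing the rule in 2.8.2 also covers a site whose own absolute LLN is below 1.5. Replacing the derived range with an age-specific absolute range would not be enough, because a correct limit can itself lie below 1.5.

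The cost is one sentence and a reordering of the grading step; no new data are needed. The downside is that some children with naturally low counts will carry a higher grade. The baseline column of the shift table will show this.

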5.6 Handling of missing or partial dates

For patients not known to have died prior to the cut-off date:

- All events with start date before or on the cut-off date, and with end date missing or after the cut-off date, or after the date of withdrawal of informed consent, will be reported as “continuing”.
- This approach applies, in particular, to AEs and concomitant medication reports. For these events, the end date will not be imputed and therefore will not appear in the listings.

If imputation of an end date is required for a specific analysis (e.g. for a dose administration record with missing end date or last date of study drug after the cut-off date), the end date will be imputed to the min(cut-off date, death date and withdrawal of informed consent date) for the purpose of calculating duration of exposure to study drug and dose intensity. The imputed date will be displayed and flagged in the listings.

5.6.1 AE date imputation

Date imputation is the creation of a new, complete date from a partial one according to an agreed and acceptable algorithm. Missing date for AE will be handled according to rules specified below. A partial date is simply an incomplete date e.g. DDOCT2001: the days are missing from this DDMMYYYY date.

Partial AE start dates, if left partial, would ultimately mean the following

It would not be possible to place the AE in time.

Therefore, the treatment/dosage at the time of the event would be unknown.

Therefore, the event could not be reported/summarized appropriately – if at all.

Therefore, it is important to perform date imputation to ensure that as many data events are represented as correctly as possible. Of course partial and/or missing dates should *also* be caught as edit checks and passed back to the investigator for resolution.

There **will be no** attempt to impute the following:

- **Missing** AE start dates
- AE start dates **missing the year**
- Partial/missing AE **end dates**

The following [Table 5-4](#) explains the abbreviations used.

Table 5-3 AE/treatment date abbreviations

	Day	Month	Year
Partial Adverse Event Start Date	<not used>	AEM	AEY
Treatment Start Date (TRTSTD)	<not used>	TRTM	TRTY

The following matrix [Table 5-5](#) describes the possible combinations and their associated imputations. In the light grey boxes, the upper_ text indicates the imputation and the lower text the relationship of the AE start date to the treatment start date (TRTSTD).

Table 5-4 AE partial date imputation algorithm

	AEM MISSING	AEM < TRTM	AEM = TRTM	AEM > TRTM
AEY MISSING	NC Uncertain	NC Uncertain	NC Uncertain	NC Uncertain
AEY < TRTY	(D) Before TRTSTD	(C) Before TRTSTD	(C) Before TRTSTD	(C) Before TRTSTD
AEY = TRTY	(B) Uncertain	(C) Before TRTSTD	(B) Uncertain	(A) After TRTSTD
AEY > TRTY	(E)	(A)	(A)	(A)

AEM MISSING	AEM < TRTM	AEM = TRTM	AEM > TRTM
After TRTSTD	After TRTSTD	After TRTSTD	After TRTSTD

The following [Table 5-6](#) is the legend to the above table.

Table 5-5 AE/treatment date relationship and imputation legend

Relationship	
Before TRTSTD	Indicates AE start date prior to Treatment Start Date
After TRTSTD	Indicates AE start date after Treatment Start Date
Uncertain	Insufficient to determine the relationship of AE start date to Treatment Start Date
Imputation Calculation	
NC / Blank	No convention/imputation
(A)	01MONYYYY
(B)	TRTSTD+1
(C)	15MONYYYY
(D)	01JULYYYY
(E)	01JANYYYY

The following [Table 5-7](#) gives a few examples.

Table 5-6 AE imputation example scenarios

Partial AE start date	Treatment start date	Relationship	Imputation Calculation	Imputed Date
12mmyyyy	20OCT2001	Uncertain	NC	<blank>
ddmmm2000	20OCT2001	Before	(D)	01JUL2000
ddmmm2002	20OCT2001	After	(E)	01JAN2002
ddmmm2001	20OCT2001	Uncertain	(B)	21OCT2001
ddSEP2001	20OCT2001	Before	(C)	15SEP2001
ddOCT2001	20OCT2001	Uncertain	(B)	21OCT2001
ddNOV2001	20OCT2001	After	(A)	01NOV2001

5.6.2 Concomitant medication date imputation

The imputation of the start date of concomitant medication will follow the same conventions as for AE date. Partial concomitant medication end dates will not be imputed.

5.6.3 Incomplete date of initial diagnosis of cancer and date of most recent recurrence

Missing day is defaulted to the 15th of the month and missing month and day is defaulted to 01-Jan.

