2.4.2 Concomitant and post therapies

The Safety set will be used for the summaries and listings of concomitant and post therapies unless otherwise specified.

Concomitant therapy

Concomitant therapies are defined as any medications (excluding study drug, prior antineoplastic treatments) and significant non-drug therapies (including physical therapy and blood transfusions) administered in the study and recorded in the Concomitant Medications/significant non-drug therapies eCRF.

These therapies will be coded using the WHO Drug Reference Listing (WHO DRL) dictionary that employs the WHO Anatomical Therapeutic Chemical (WHO ATC) classification system. All summaries will be tabulated using frequency counts and percentages.

Concomitant therapies will be summarized by ATC class and preferred term. These summaries will include 1) medications and non-drug therapies starting on or after the start of study drug but starting no later than 30 days after last dose of study drug and 2) medications and non-drug therapies starting prior to the start of study drug but continuing after the start of study drug.

All therapies will be listed. Any therapies starting and ending prior to the start of study drug or starting more than 30 days after the last date of study drug will be flagged in the listing.

Frequency and percentage of patients using medications known to prolong the QT interval concomitantly with study drug will be summarized by ATC class and preferred term.

Antineoplastic therapy after discontinuation of study drug

All summaries will be tabulated using frequency counts and percentages using the FAS.

Antineoplastic therapies, including medications, surgeries, and radiotherapies, initiated after discontinuation of study drug will be summarized and listed by Anatomical Therapeutic Chemical (ATC) class and preferred term.

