5.6.4 Incomplete date for anti-neoplastic therapies

Prior therapies

Start date:

The same rule which is applied to the imputation of AE/concomitant medication start date will be used with the exception that for scenario (B) will be replaced to be 'start date of study drug -1'.

End date:

Imputed date = min (start date of study drug, last day of the month), if day is missing;

Imputed date = min (start date of study drug, 31DEC), if month and day are missing.

If the end date is not missing and the imputed start date is after the end date, use the end date as the imputed start date.

If both the start date and the end date are imputed and if the imputed start date is after the imputed end date, use the imputed end date as the imputation for the start date.

Post therapies

Start date:

Imputed date = max (last date of study drug + 1, first day of the month), if day is missing;

Imputed date = max (last date of study drug + 1, 01JAN), if day and month are missing.

End date: No imputation.

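### Partial start dates set to first dose + 1 are not checked against a recorded end date, so adverse events and medications known to have ended before treatment can be counted as on-treatment or concomitant

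*SAP*

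**What the plan says.** The matrix in SAP 5.6.1 (Tables 5-4 to 5-6) imputes a partial adverse event start from its year and month relative to first dose. Rule (B), first dose + 1 day, covers two cells, both with the start year equal to the first-dose year: month missing, and month equal to the first-dose month. Both are labelled uncertain, which the legend explains as "Insufficient to determine the relationship of AE start date to Treatment Start Date". The recorded end date is not an input. The only mention of end dates is that "Partial/missing AE end dates" are not imputed.

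SAP 5.6.2 carries the rule over to medications: "The imputation of the start date of concomitant medication will follow the same conventions as for AE date". It adds: "Partial concomitant medication end dates will not be imputed".

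SAP 5.6.4, for prior antineoplastic therapy only, replaces rule (B) by the day before first dose and adds a check: "If the end date is not missing and the imputed start date is after the end date, use the end date" as the imputed start.

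The imputed dates are used in these places:

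- SAP 2.8 starts the on-treatment period on the day of first dose. SAP 2.1 restricts safety tables to that period unless stated otherwise.
- SAP 2.4.2 has two groups of concomitant therapy. The first is defined by a start on or after first dose (up to 30 days after the last), with no condition on the end. The second needs an earlier start and continuation into treatment.
- The listing flag in SAP 2.4.2 covers this case: "Any therapies starting and ending prior to the start of study drug". It also covers therapies starting more than 30 days after the last dose.

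**The concern.** Placing a start on treatment is a reasonable default when its relation to first dose is unknown. It stops being reasonable when the end date is recorded and falls before first dose, because the record then cannot have started on treatment. The rule overrides known data and creates an interval that begins after it ends.

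Such records are to be expected. Protocol 8.1.1 records adverse events from consent, and screening runs from day -28 to day -1, so an event can start and resolve before dosing. Protocol exclusion criteria 14 and 15 and section 6.4.2 require several drug classes to be stopped at least a week before first dose, so medications that end shortly before treatment will be in the database.

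At stake is the accuracy of the adverse event tables, the concomitant medication table and the summary of QT-prolonging drugs used together with study drug. The last matters because the protocol restricts such drugs, and an entry created by imputation could look like a deviation.

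**Working it through.** **1. Reproduce the SAP's own examples.** The matrix was coded with A = first of the month, B = first dose + 1, C = 15th of the month, D = 1 July, E = 1 January, and blank where the year is missing. With first dose on 20OCT2001, all seven rows of Table 5-6 reproduce. Both ddOCT2001 and ddmmm2001 give 21OCT2001.

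**2. Add a known end date (first dose 20OCT2001).**

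| Recorded start | Recorded end | Rule | Imputed start | Start minus end | Class as written | Class with the 5.6.4 check |
|---|---|---|---|---|---|---|
| ddOCT2001 | 15OCT2001 | B | 21OCT2001 | +6 days | on-treatment | pre-treatment (start 15OCT2001) |
| ddmmm2001 | 31MAR2001 | B | 21OCT2001 | +204 days | on-treatment | pre-treatment (start 31MAR2001) |
| ddOCT2001 | 20OCT2001 | B | 21OCT2001 | +1 day | on-treatment | on-treatment (start 20OCT2001) |
| ddOCT2001 | missing | B | 21OCT2001 | n/a | on-treatment | unchanged |
| ddOCT2001 | 05NOV2001 | B | 21OCT2001 | negative | on-treatment | unchanged |
| ddSEP2001 | 10SEP2001 | C | 15SEP2001 | +5 days | pre-treatment | pre-treatment (start 10SEP2001) |

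**3. General result.** Let T be first dose and E the known end. Rule (B) gives S = T + 1. If E is before T, then E ≤ T - 1, so S - E ≥ 2 days and S is after T. Every such record has its start after its end and falls in the on-treatment window.

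Enumeration over all first-dose dates in a 365-day year, with every possible earlier end date, agrees:

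- Month missing: 365 × 364 / 2 = 66,430 combinations.
- Month equal to the first-dose month: 7 × 465 + 4 × 435 + 378 = 5,373.
- Total 71,803. All are on-treatment as written; none are after the check.

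This shows that the result is certain within the subset. It is not a frequency in the data.

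**4. Confined to rule (B).** For the other cells, 6,762 combinations of first dose and partial start (first-dose year or the year before) allow a start before first dose. None is imputed to first dose or later. Rules (C) and (D) can also put a start after its own end, as in the last table row, but the class stays correct.

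**5. Partial end dates.** Take start ddmmm2001 and end ddMAR2001, with first dose 20OCT2001. The end month settles that the record is pre-treatment, but partial ends are not imputed, so a check that needs a complete end date would miss it.

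**6. Consequence in SAP 2.4.2.** By its true dates, a drug stopped before first dose belongs to neither group of concomitant therapy. With the imputed start it meets the first. Because the listing flag needs both start and end before first dose, the flag is lost as well.

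**7. Separate minor point, SAP 5.6.3.** For cancer diagnosis and recurrence: "Missing day is defaulted to the 15th of the month and missing month and day is defaulted to 01-Jan". There is no bound at first dose. A recurrence in the month of a first dose on the 10th is dated the 15th, 5 days after treatment began (5 / 30.4375 = 0.16 months). The most this can be is 14 days, or 0.46 months. The 1 January default can also precede birth for a child diagnosed in the birth year.

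**The case against.** The strongest reply is that rule (B) is a deliberate, conservative safety convention, and that SAP 5.6.1 also sends partial dates back to the investigator as edit checks. Both points are fair. The convention stands for records whose timing is truly unknown, and queries will reduce the number affected. Neither corrects the rule for a record left unresolved whose end date already answers the question.

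Second, adverse event exposure is narrow. An affected event must start and end between consent and first dose and have an unresolved partial start. The SAP also does not say outright that events are assigned to a period by start date. That is an inference, though a safe one: 5.6.1 gives placing the event in time as the reason for imputing, and 5.1 applies the data cut-off by event start date.

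Third, SAP 2.4.2 first describes concomitant therapies as those given in the study, and the QT summary as use together with study drug. A programmer might exclude a drug stopped months earlier on that wording. The operative grouping still depends on the start date alone, so inclusion in the QT summary is possible rather than certain.

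A reader might also infer more than the documents support:

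- That every partial start in the first-dose year is moved. A known different month goes to rule (A) or (C), as the ddSEP2001 and ddNOV2001 examples show.
- That a first dose on 31OCT2001, which turns ddOCT2001 into 01NOV2001, is a further misclassification. Holding the date at 31OCT2001 would still be on-treatment, so no class changes.

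**Conclusion.** The point holds in a limited form. Rule (B) has no end-date check in SAP 5.6.1 or 5.6.2. Any rule (B) record with a known end before first dose gets a start after its own end and is treated as on-treatment (adverse events) or as begun on treatment (medications). Within that subset the error is certain and one-directional, toward over-counting.

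The size of the subset cannot be derived. The documents give no rate of partial start dates and no count left after query, so no number of affected events or drugs is claimed. Adverse events are exposed mainly through the screening window. Medications may be more exposed, because they can start much earlier.

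A reader might infer that the trial's safety profile is materially inflated, or that dose finding is touched. The documents support neither. DLTs are defined within the first 21 days of treatment and reviewed at dose-decision meetings, and the SAP already states the MTD/RDE as 510 mg/m² fasted and 500 mg/m² fed. Response and PFS do not use these imputed dates. This is a low-severity correction to descriptive safety and medication tables. The SAP 5.6.3 point is smaller still and affects only descriptive intervals.

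**What to change.** Add the following to SAP 5.6.1 and 5.6.2:

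- If the end date is complete and the imputed start is later, use the end date as the imputed start. This is the check already in SAP 5.6.4.
- If the end date is partial and its recorded month or year is already before first dose, class the record as pre-treatment, for example by holding the imputed start at the last day of the recorded end month. A partial end in the first-dose month does not settle the matter, so rule (B) stays.

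Records without such a conflict keep rule (B) and do not change.

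In SAP 5.6.3, cap the imputed diagnosis or recurrence date at first dose and floor it at date of birth.

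The cost is a few sentences in the SAP and minimum/maximum conditions in the date derivations, with no new data collection. Listing the records whose class changes would show the actual size of the problem.
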